10.3.2. Noncompartmental Analysis Population AUC and Percent Penetration Estimation

The median concentrations of fosfomycin from the BAL sampling times will be used to estimate the population average AUC_{0-8} of plasma, ELF, and AM will be estimated using the Linear Up Log Down calculation method.

The ratios of population average AUC₀₋₈ of ELF-to-plasma and AM-to-plasma will be calculated to determine estimates of the percent penetration by dividing the AUC₀₋₈ for ELF or AM by the geometric mean Plasma AUC₀₋₈.

Summary statistics for all continuous PK measures and parameters will include mean, SD, min, max, median, coefficient of variation as a percent (CV%), GM, and geometric SD (GSD), unless otherwise specified. CV% will not be calculated for T_{max} and T_{last} since those variables are not log-normal.

The CV% will be calculated using the method for log-normally distributed data.:

 $CV\% = \sqrt{\exp(\sigma^2) - 1} * 100\%$, where σ^2 is the variance of the log-transformed data [5].

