4.2. Discussion of Study Design, Including the Choice of Control Groups

As the main focus of this protocol is to evaluate the safety and pharmacokinetics of multiple doses of ZTI-01, there is no control group and all subjects receive the same dose of ZTI-01with the same PK blood collection timepoints. Subjects will be randomized to one of five BAL sampling timepoints with a total of 6 subjects assigned to each BAL sampling time.

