4.4.3. Method of Assigning Subjects to BAL Sampling Timepoint Groups (Randomization)

Subjects will be randomized to a single standardized bronchoscopy with BAL sampling timepoint upon study enrollment using an assignment schedule as follows: 30 subjects will be randomized 1:1:1:1:1 to one of the five BAL sampling timepoints (30 minutes, 75 minutes, 2 hours, 5 hours, or 8 hours after the start of the third IV infusion of ZTI-01). Up to six (6) subjects will be enrolled as alternates. Alternates will arrive at DEPRU on Day -1 to Day 1 and will adopt the planned BAL sampling timepoint of any other enrolled subject who fails to present for check-in or who fails to meet inclusion/exclusion criteria on Day -1 to Day 1. If all

scheduled subjects present for check-in and meet Day -1 to Day 1 inclusion/exclusion criteria, then alternates will not undergo any further study procedures at that time. In that case, alternates may be assigned to a new bronchoscopy time on a future date, alternate status for a future date, or as replacement subjects.

Subjects will be enrolled online using the enrollment module of AdvantageEDCSM software. The randomization code will be prepared by DCC statisticians and included in the enrollment module for this study. AdvantageEDC will assign each subject to a sampling timepoint after the demographic and eligibility data have been entered.

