4.5.2. Pharmacokinetics Variables

Blood (plasma) for PK samples will be drawn for all subjects at the following timepoints relative to each dose:

- Dose 1: Within 10 minutes before starting the 1-hour infusion and at 30 minutes (±5 minutes), 1 hour (0 to 5 minutes from end of infusion), 1 hour 15 minutes (±5 minutes), 2 hours (±5 minutes), 5 hours (±15 minutes) from the start time of the first infusion of ZTI-01
- Dose 2: Within 10 minutes before starting the second 1-hour infusion.

Note: This PK sample will be reported as the 8 hours post Dose 1 PK sample

Dose 3: Within 10 minutes before starting the 1-hour infusion and at 30 minutes (±5 minutes), 1 hour (0 to 5 minutes from end of infusion), 1 hour 15 minutes (±5 minutes), 2 hours (±5 minutes), 5 hours (±15 minutes), 8 hour (±15 minutes), and 12 hours (±15 minutes) from the start time of the third (last) infusion of ZTI-01

A standardized bronchoscopy with BAL sampling will be performed at ± 15 minutes of the single assigned timepoint based on each subject's schedule assignment: 30 minutes, 1 hour 15 minutes, 2, 5, or 8 hours after the start time of the third (last) infusion of ZTI-01.

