5. SAMPLE SIZE CONSIDERATIONS

Since statistical analyses are not intended to serve as a basis of definitive conclusions, statistical power considerations for determination of sample size were not performed. The sample size for this study was selected as adequate for determining the safety and PK of ZTI-01. The sample size is based on clinical experience and judgment relative to study design and objectives.

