10.4.3. Analysis of Noncompartmental Analysis Parameters and Percent Penetration

The NCA population average AUC₀₋₈ of plasma, ELF, and AM using the median concentrations of fosfomycin from the BAL sampling times will be presented in Table 43 along with the calculated percent penetration for ELF to plasma and AM to plasma.

Data will be presented graphically in the following figures:

- Box plot showing BAL sampling timepoint on the x-axis and the distribution of subject fosfomycin concentrations in ELF, AM, and plasma at matching BAL timepoint on the y-axis (Figure 50).
- Linear plots showing the population median fosfomycin concentrations by compartment (plasma, ELF, and AM) across each of the BAL sampling timepoints (Figure 51).
- Semi-logarithmic plots showing the population median fosfomycin concentrations by compartment (plasma, ELF, and AM) across each of the BAL sampling timepoints (Figure 52).

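### The SAP gives no time-0 rule for the lung AUC0-8 and names two plasma denominators, so percent penetration is not uniquely defined and is understated under one reading

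*SAP*

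**What the plan says.** SAP 4.5.2 schedules the single BAL at "30 minutes, 1 hour 15 minutes, 2, 5, or 8 hours after the start time of the third (last) infusion of ZTI-01", and SAP 4.4.3 lists the same five times. SAP 4.2 puts six subjects at each. No lung specimen is taken before Dose 3. Plasma, by contrast, is drawn from every subject in the 10 minutes before Dose 3.

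SAP 10.3.2 gives the inputs for all three matrices: "The median concentrations of fosfomycin from the BAL sampling times will be used to estimate the population average" AUC0-8, and the area "will be estimated using the Linear Up Log Down calculation method". SAP 10.4.3 repeats that the AUC0-8 "of plasma, ELF, and AM using the median concentrations of fosfomycin from the BAL sampling times will be presented in Table 43". Protocol 11.3 agrees. The second paragraph of SAP 10.3.2, however, obtains percent penetration by dividing the AUC0-8 "for ELF or AM by the geometric mean Plasma" AUC0-8.

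SAP 10.3 lists the WinNonlin settings for plasma and pulmonary data and has no start-point entry. SAP 10.1 rules out imputing missing concentrations in the NCA. Its zero rule covers only measured samples below the LLOQ that precede the first quantifiable one.

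**The concern.** An area from 0 to 8 h cannot be computed from points that begin at 0.5 h without a start-point rule. Two simple defaults are to integrate from 0.5 h only, or to start at zero. The first gives AUC0.5-8 under an AUC0-8 label. The second treats Dose 3 as a first dose, although the SAP itself plans accumulation ratios.

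The choice matters because of the denominator. A median profile yields one AUC, so a geometric mean plasma AUC0-8 only makes sense over individual subjects' AUCs, and those include the measured pre-dose value. On that reading the denominator holds the first half hour and the numerator may not. ELF and AM penetration is the trial's intrapulmonary outcome, and two analysts following the SAP could report different values from the same data.

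**Working it through.** The documents give no AUC, trough, half-life or penetration figure, so there is nothing to reproduce. The size has to be modelled.

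**From the documents:** three 6 g, 1-hour infusions every 8 h; BAL at 0.5, 1.25, 2, 5 and 8 h; plasma over 0-8 h after Dose 3 at 0, 0.5, 1, 1.25, 2, 5 and 8 h; Linear Up Log Down.

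**Assumed, not from the documents:** one-compartment plasma with half-life 1.5-4 h; lung following the SAP 10.5 effect-site form, dC/dt = Q(Cp - C), with equilibration half-life (lag) 0.1-24 h. Volume (20 L here) and a lung partition factor of 1 cancel from the relative errors.

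**Formulas.** Rising segment: Δt(C1 + C2)/2. Falling segment: Δt(C1 - C2)/ln(C1/C2). Error = (estimated lung/plasma AUC ratio)/(true ratio) - 1.

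**Worked case: plasma half-life 2 h, lung lag 1 h (µg/mL)**

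| Time (h) | 0 | 0.5 | 1 | 1.25 | 2 | 5 | 8 |
|---|---|---|---|---|---|---|---|
| Plasma | 23.8 | 157.7 | 270.4 | 247.9 | 191.2 | 67.6 | 23.9 |
| Lung | 44.2 | 59.6 | 106.2 | 130.5 | 165.1 | 108.0 | 44.4 |

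Lung, 0.5-8 h from the BAL times: 71.3 + 110.9 + 403.6 + 214.7 = 800.5.
- Zero start adds 0.25 × 59.6 = 14.9, giving 815.4.
- The 8 h value at time 0 adds 0.25 × (44.4 + 59.6) = 26.0, giving 826.5.

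Plasma, 0.5-8 h from the BAL times: 152.1 + 163.7 + 356.6 + 126.1 = 798.5.
- Zero start adds 39.4 (838.0, from unrounded values).
- The 8 h value adds 45.4 (844.0, from unrounded values).
- The full plasma schedule gives 863.6.

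True areas are 865.1 (lung) and 865.4 (plasma), a true ratio of 0.9997.

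| Time-0 handling | Full-profile plasma | Matched BAL-time plasma |
|---|---|---|
| 0-0.5 h dropped | 800.5/863.6 = 0.927 (-7.3%) | 800.5/798.5 = 1.002 (+0.3%) |
| Zero start | 815.4/863.6 = 0.944 (-5.6%) | 815.4/838.0 = 0.973 (-2.7%) |
| 8 h value | 826.5/863.6 = 0.957 (-4.3%) | 826.5/844.0 = 0.979 (-2.0%) |

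In this case the true time-0 value (44.2) also leaves -4.3% against the full profile. That remainder is the cost of five sparse lung points set against a richer plasma profile. Time-0 handling accounts for 7.3 - 4.3 = 3.0 points (dropped) or 5.6 - 4.3 = 1.3 points (zero start).

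**Across the assumed ranges, error in percent penetration**

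| Time-0 handling | Full-profile plasma | Matched plasma |
|---|---|---|
| Dropped | -7.4% to -4.5% | -0.9% to +4.5% |
| Zero start | -5.9% to -1.7% | -2.7% to +1.7% |
| 8 h value | -4.9% to +0.4% | -2.1% to +3.3% |

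How finely the half-lives are gridded moves these ends by about 0.2 point at most. Against the full profile, time-0 handling alone contributes about 2.4-5.1 points (dropped) or 0.4-2.6 points (zero start). The 8 h value comes within about 1 point of using the true time-0 value, and within 0.3 point for lags up to 4 h.

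**The case against.** A reader might infer that the SAP discards the first half hour or sets it to zero, and that penetration is therefore always understated. The documents do not support this. The SAP prescribes neither rule. Its bar on imputation concerns missing samples, and its zero rule concerns measured samples below the LLOQ; an unscheduled time falls under neither. Protocol 11.3 also defers details to a PK analysis plan, which may be this SAP or a document not available here. Most of the text (Protocol 11.3, SAP 3.2, the first paragraph of 10.3.2, and 10.4.3) builds plasma from the same BAL times. The gap is then in both numerator and denominator, and with the interval dropped most modelled cases err slightly upward.

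Materiality is also modest. Each median rests on six subjects, the BAL window is ±15 minutes, and the study is descriptive: "statistical power considerations for determination of sample size were not performed". The exploratory population PK analysis in SAP 10.5 integrates full 8-hour profiles without needing a BAL at time 0.

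Nor is the proposed fix free of error. With matched plasma its benefit is a defined 0-8 h quantity, not a uniformly smaller error. For a lung matrix with a 24 h lag, the 8 h value overstates the pre-dose value and leaves +1.5% to +3.3%, while a zero start happens to land within ±0.4%.

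All of this stands. It limits the size and direction of the effect. It does not supply the missing rule or resolve the two denominators.

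**Conclusion.** The point holds as a defect of specification with a conditional bias. The SAP labels the lung result AUC0-8, gives no time-0 rule, and names two plasma denominators. Penetration is understated in every modelled case only when a lung area that omits 0-0.5 h or starts at zero is divided by the full-profile plasma AUC: by about 4.5-7.4% or 1.7-5.9% respectively. Roughly 2-5 and 0.4-3 points of that are due to time-0 handling, and the rest to sparse lung sampling. With matched plasma the error is a few percent in either direction. All sizes rest on assumed kinetics (plasma half-life 1.5-4 h, lung lag 0.1-24 h). The issue is minor for a descriptive trial, but it is cheap to settle before database lock.

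**What to change.** In SAP 10.3.2 and the Table 43 footnote:

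- State that the time-0 value for ELF and AM is that matrix's 8 h median, because dosing is every 8 h.
- State that the plasma AUC0-8 used as denominator is built from the same BAL-time medians with the same time-0 rule.
- Remove the geometric-mean denominator, or reconcile it with 10.4.3 and Protocol 11.3.
- Report the plasma 8 h median beside the observed pre-Dose 3 plasma median as a check on the rule.
- Add a sensitivity analysis that uses the observed plasma pre-dose value at time 0. In the model this moves the result by about 0.1 point or less.
- Note that for a matrix that equilibrates very slowly the 8 h value slightly overstates the pre-dose value, with a matched-denominator error of up to about +3%.

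The cost is a few sentences and one extra table line. No samples, visits or procedures change.

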# 5.3. Treatment Assignment Procedures

#### 5.3.1. Randomization Procedures

Subjects will be randomized to a single standardized bronchoscopy with BAL sampling timepoint upon study enrollment using an assignment schedule as follows: 30 subjects will be randomized 1:1:1:1:1 to each of the five BAL sampling timepoints (30 minutes, 75 minutes, 2 hours, 5 hours, or 8 hours after the start of the third IV infusion of ZTI-01). Up to ten (10) subjects will be enrolled as alternates. Alternates will arrive at DEPRU on Day -1 to Day 1 and will adopt the planned BAL sampling timepoint of any other enrolled subject who fails to present for check-in or who fails to meet inclusion/exclusion criteria on Day -1 to Day 1. If all scheduled subjects present for check-in and meet Day -1 to Day 1 inclusion/exclusion criteria, then alternates will not undergo any further study procedures at that time. In that case, alternates may be assigned to a new bronchoscopy time on a future date, alternate status for a future date, or as replacement subjects (see Section 5.3.4).

Subjects will be enrolled online using the enrollment module of AdvantageEDCSM software. The randomization code will be prepared by DCC statisticians and included in the enrollment module for this study. AdvantageEDCSM will assign each subject to a sampling timepoint after the demographic and eligibility data have been entered.

Instructions for use of the enrollment module are included in the AdvantageEDCSM User's Guide. Manual back-up procedures and instructions are provided for use in case the site temporarily loses Internet access or the online enrollment system is unavailable.

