#### 8.2.3. Pharmacokinetic Blood and BAL Samples

An assay to measure ZTI-01 concentrations in plasma, BAL, and cell pellet samples and urea in plasma and BAL samples will be conducted at a central analytical lab using a validated LC-MS/MS bioanalytical assay. Timing of samples will be with respect to the start of each dose of study drug (pre-dose and postinfusion start, when applicable). The date and time of each PK sample and BAL collection will be recorded in the eCRF. Blood PK samples will be drawn for all subjects within the following windows: -10 to -1 minute for scheduled samples at pre-dose;  $\pm 5$  minutes for scheduled samples at 30 minutes, 1 hour 15 minutes, and 2 hours; +0-5 minutes from end of infusion for the scheduled sample at 1 hour; and  $\pm 15$  minutes for scheduled samples at 5, 8, and 12 hours. BAL samples for PK (fosfomycin and urea assays) will be obtained within +/- 15 minutes of the assigned sampling time.

Instructions for collecting, processing, storage, and shipping of plasma, BAL, and urine samples will be provided in the MOP.

Blood and BAL samples are summarized in Table 7.

Study day	Dosing	Blood sampling times*	BAL sampling times §
Day 1-2 Dosing ZTI-01 6 g IV infusion over 1 hour (+10 minute window)		All subjects: Pre-dose (-10 to -1 minutes), 30 minutes (during the 1-hour infusion), and 1 hour, 1 hour 15 minutes, 2, and 5 hours after the start of the first dose	No sampling
	Second dose: ZTI-01 6 g IV infusion over 1 hour (+10 minute window)	All subjects: Pre-dose (-10 to -1 minutes)	No sampling
	Third dose: ZTI-01 6 g IV infusion over 1 hour (+10 minute window)	All subjects: Pre-dose (-10 to -1 minutes), 30 minutes (during the 1-hour infusion), and 1 hour, 1 hour 15 minutes, and 2, 5, 8, and 12 hours after the start of the third (last) infusion of ZTI-01	Each subject: Complete a single bronchoscopy with BAL at one of the five sampling times: 30 minutes (during the 1-hour infusion), 1 hour 15 minutes, 2, 5, or 8 hours from the start of the third (last) infusion of ZTI-01
Day 2 At Discharge	No further dosing	All subjects: 12 hours after the start of the third (last) infusion of ZTI-01	No sampling
* Blood PK samp	les will be drawn for all subjects	within the following windows: -10	to -1 minutes for scheduled

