Intrapulmonary PK of ZTI-01 will be derived as follows. Serum and BAL urea measurements will be used to estimate the volume of ELF recovered in the BAL samples. The ratios of ELF and AM concentrations of fosfomycin to simultaneous plasma concentrations will be calculated for each subject and summarized for each sampling time. The median concentrations of fosfomycin from the BAL sampling times will be used to estimate the population average AUC0-8 of plasma, ELF, and AM. The

DMID/NIAID/NIH

Version 9.0

27 August 2020

ratio of population average  $AUC_{0-8}$  of ELF-to-plasma and AM-to-plasma will be calculated to determine the percent penetration.

Specific details of pharmacokinetic analysis will be included in the study-specific pharmacokinetic analysis plan.

DMID/NIAID/NIH

CONFIDENTIAL

27 August 2020

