3.2. Endpoints

Safety:

- The safety outcome measure will be the occurrence of adverse events (AEs), summary of physical exam findings, vital signs, clinical laboratory tests, and electrocardiogram (ECGs) at any time from the start of study drug administration through the end of subject follow-up.
- All subjects who receive at least one dose of study drug will be included in the safety outcome measure. AEs will be collected from the time of dosing on Day 1 through the telephone follow-up interview on Day 3. Treatment Emergent Adverse Events (TEAEs) will be assessed by severity and relationship to the study drug as determined by the investigator.

Pharmacokinetics:

- The pharmacokinetic outcome measures will be plasma and intrapulmonary concentrations of ZTI-01 by validated bioassays.
- Plasma PK parameters will be derived from the plasma concentration vs. time curves after the third dose of study drug. The parameters include, but are not limited to:
- Maximum measured plasma concentration (C_{max})
- Area under the concentration vs. time curve (AUC₀₋₈ and AUC_{0-inf})
- Time to peak concentration (t_{max})
- Terminal elimination half-life $(t_{1/2})$
- \circ Terminal-phase elimination rate constant (λ_z)
- Volume of distribution (V_d)
- Clearance (CL)

Intrapulmonary PK parameters will be derived from the ratios of drug concentrations in ELF and AMs to simultaneous drug concentrations in plasma for each subject and summarized for each sampling time. The median concentrations of fosfomycin from the BAL sampling times will be used to estimate the AUC₀₋₈ of plasma, ELF, and AM. The ratios of AUC₀₋₈ of ELF-to-plasma and AM-to-plasma will be calculated to determine the percent lung penetration.

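### SAP 10.3.2 divides the median-based ELF or AM AUC0-8 by a geometric mean plasma AUC0-8, which conflicts with the protocol's definition of percent penetration and with the SAP's own

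*SAP*

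**What the plan says.** **Protocol.** Section 11.3 states: "The median concentrations of fosfomycin from the BAL sampling times will be used to estimate the population average" exposure over 0-8 h in each of the three matrices. Of the resulting ratios it says: "ELF-to-plasma and AM-to-plasma will be calculated to determine the percent penetration". Section 3.2 gives the same definition.

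**SAP, agreeing with the protocol.** Section 3.2 (Endpoints) begins its definition in the same way: "The median concentrations of fosfomycin from the BAL sampling times will be used to estimate the" areas for all three matrices. Section 10.4.3 says of the noncompartmental areas that those "of plasma, ELF, and AM using the median concentrations of fosfomycin from the BAL sampling times will be presented in Table 43", and the penetration percentages appear beside them.

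**SAP, departing from it.** Section 10.3.2 opens with the median construction for all three matrices, plasma included. Its next paragraph then obtains percent penetration by a division of areas, "for ELF or AM by the geometric mean Plasma" area.

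**Sampling times.** BAL is taken at "30 minutes, 75 minutes, 2 hours, 5 hours, or 8 hours after the start of the third IV infusion of ZTI-01" (Protocol 5.3.1), six subjects per time. Dose-3 plasma is sampled in every subject at pre-dose, 0.5, 1, 1.25, 2, 5, 8 and 12 h (SAP 4.5.2 and 10.2).

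**The concern.** One outcome has two formulas. A programmer who follows SAP 10.3.2 departs from the protocol's outcome definition. One who follows Protocol 11.3 departs from the SAP's operative paragraph. Nothing in the SAP presents the geometric mean as a deliberate change, and the median-based plasma AUC that 10.3.2 builds is then not used in its own ratio.

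The two denominators also differ in kind. One is the area under a single curve through medians at five times. The other averages individual areas that include a pre-dose sample and the end-of-infusion sample at 1 h, neither of which exists for BAL. The grid difference therefore enters the ratio, and a reader dividing the ELF row by the plasma row described in 10.4.3 would not recover the printed percentage.

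**Working it through.** The plan states no penetration value, AUC or half-life, so there is no figure to reproduce. The check has three parts.

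**1. What the geometric mean can refer to.** The median-curve AUC0-8 is one number per matrix, so it has no geometric mean. The only geometric means of plasma AUC0-8 in the SAP are those of individual noncompartmental AUCs: Table 37 (dose 1) and Table 38 (dose 3). Section 10.3.2 names no dose; the Table 43 footnote says dose 3. Individual AUCs use each subject's plasma profile at actual times (SAP 10.3). That they use the fuller grid is an inference from 10.2 and 10.3, not a statement in 10.3.2.

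**2. Grid effect for identical concentrations.** Assumptions not in the documents: one compartment, half-life 1.5-4 h, V = 20 L (V cancels in every ratio). From the documents: 6 g over 1 h every 8 h, third dose, linear-up log-down rule. For each dose, with k = ln 2 / half-life and s the time since its start:

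- during infusion: C = (6000/kV)(1 - e^(-ks))
- afterwards: C = (6000/kV)(1 - e^(-k)) e^(-k(s-1))

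Contributions of the three doses are summed. With half-life 2 h, C at 0, 0.5, 1, 1.25, 2, 5 and 8 h is 23.8, 157.7, 270.4, 247.9, 191.2, 67.6 and 23.9 mg/L.

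- Full grid segments: 45.4 + 107.0 + 64.7 + 163.7 + 356.6 + 126.1 = 863.6 (unrounded sum).
- BAL grid, 0.5 to 1.25 h: 0.75 × (157.7 + 247.9)/2 = 152.1, against 107.0 + 64.7 = 171.7 on the full grid. The missing 1 h peak costs 19.6.
- BAL grid total with time 0 set to the 8 h value: 844.0, so 844.0/863.6 = 0.977.
- BAL grid total with time 0 set to zero: first segment 0.5 × 157.7/2 = 39.4, total 838.0, so 838.0/863.6 = 0.970.

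| Half-life (h) | Time 0 = 8 h value | Time 0 = zero |
|---|---|---|
| 1.5 | 0.969 | 0.966 |
| 2 | 0.977 | 0.970 |
| 2.5 | 0.982 | 0.972 |
| 3 | 0.985 | 0.973 |
| 4 | 0.989 | 0.974 |

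A fluid with exactly plasma's concentrations would thus read about 97-99% instead of 100%.

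**3. Difference within one trial.** Let A be the median-based AUC and G the geometric mean plasma AUC. The SAP 10.3.2 ratio is A(ELF)/G and the protocol ratio is A(ELF)/A(plasma). Dividing the first by the second gives A(plasma)/G, so the ELF data cancel. I simulated 30 subjects, six per BAL time, with half-life 2, 3 or 4 h and between-subject CV of 20% or 30% on k and V (assumed), 1,000 trials per scenario.

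| Plasma medians from | Time 0 | Median of A(plasma)/G across scenarios | Widest 5th-95th percentiles |
|---|---|---|---|
| Six matched subjects per time | zero | 0.976-0.987 | 0.877-1.099 |
| Six matched subjects per time | 8 h value | 0.983-1.002 | 0.885-1.113 |
| All 30 subjects | zero | 0.967-0.977 | 0.895-1.053 |
| All 30 subjects | 8 h value | 0.974-0.992 | 0.901-1.070 |

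The wide limits come from the 30% CV. At 20% with matched subjects they run from 0.910 to 1.064. For a true ELF penetration of 50% (time 0 = zero, matched subjects, ELF log-scale noise SD 0.3), the median estimate was 50.1-50.6% with the protocol ratio and 49.0-49.9% with the geometric mean.

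**The case against.** The strongest reply is that this hardly matters. The average shift is a few percent at most. The study tests no hypothesis, its analyses are not meant to support definitive conclusions (Protocol 11.2), and SAP 10.5 adds an exploratory model that computes plasma and lung AUCs in a consistent way. Nor is the protocol ratio exact. With a lagged ELF of the effect-site form in SAP 10.5 (assumed half-life 1.5-4 h, rate constant Q 0.3-5 per h), reported over true penetration was 0.954-0.997 with the geometric mean and 0.982-1.019 with the median-based denominator. At Q = 5 the geometric-mean version was the closer of the two. All of this stands, and it rules out any claim of serious bias. It does not remove the two formulas for one outcome.

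Three stronger readings are tempting but unsupported:

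- **A bias of 6-9%.** This arises only if the sparse curve's area starts at 0.5 h (ratio 0.911-0.939). The plan specifies AUC0-8. The missing time-0 rule is a separate gap, not a result of the geometric-mean denominator.
- **The Table 43 shell contradicts 10.3.2.** The shell states neither a denominator nor a construction. The conflict is with the text of 10.4.3.
- **The BAL window aggravates this.** Protocol 8.2.3 says that "BAL samples for PK (fosfomycin and urea assays) will be obtained within +/- 15 minutes of the assigned sampling time", a wider window than for the early plasma samples. That bears on the per-subject concentration ratios, not on this denominator, and actual times are recorded.

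**Conclusion.** The inconsistency is real and can be read directly from the text. SAP 10.3.2 conflicts with Protocol 3.2 and 11.3, with SAP 3.2 and 10.4.3, and with its own opening sentence. It should be settled before analysis because it determines how a stated PK outcome is calculated. Its expected numerical effect is small: about 0-3% on average, given a time-0 value. In a single trial the two definitions can differ by roughly 10% either way when plasma medians come from six subjects per time and CV is 30%, and by less at 20% CV or, on the upper side, with all 30 subjects. These sizes rest on the assumed one-compartment model, half-life and CVs; the contradiction does not depend on them.

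**What to change.** In SAP 10.3.2, replace the geometric mean denominator with the dose-3 population average plasma AUC0-8 from median plasma concentrations at the five BAL times. Use the same linear-up log-down method and one stated time-0 rule for plasma, ELF and AM. State whether the plasma medians use only the subjects with BAL at that time or all evaluable subjects, since the documents leave this open.

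Keep the geometric mean AUC0-8 as a plasma parameter in Table 38. If a penetration based on it is wanted, show it only as a labelled sensitivity analysis. A Table 43 footnote naming the denominator would help.

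The cost is a few lines of SAP wording and minor programming, with no new data. It must be done before data lock, because SAP 15 rules out amendment afterwards.
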